4. SUBJECT POPULATION

4.1. Number of Subjects and Subject Selection

100 subjects to receive treatment with Tenofovir DF and assigned to one of two monitoring groups (50 in each group). The subjects will be assigned to one of two monitoring groups using a validated computer-generated tool for randomization. Subjects will be assigned to Group 1 or 2 upon enrollment into the study but prior to Baseline laboratory and DEXA imaging assessments.

4.2. Inclusion Criteria

Subjects must meet *all* of the following inclusion criteria to be eligible for participation in this study.

- 1) 12 to <16 years of age
- 2) Documented chronic HBV infection (e.g. positive serum HBsAg \geq 6 months)
- 3) Weight \geq 35 kg
- 4) Able to swallow oral tablets
- 5) Negative serum β -HCG pregnancy test (for females of childbearing potential, see [Appendix 5](#))
- 6) Estimated glomerular filtration rate (creatinine clearance) \geq 80 mL/min/1.73m²

Estimated creatinine clearance using Schwartz Formula
(mL/min/1.73m²) = k \times L/Scr

[(k is a proportionality constant: for adolescent females \geq 12 years old, k = 0.55, and for adolescent males \geq 12 years, k = 0.70); L is height in centimeters (cm); and Scr is serum creatinine (mg/dL)]

- 7) Parent or legal guardian of potential study subjects able to provide written informed consent prior to any screening evaluations and willing to comply with study requirements or subject able to provide written assent as determined by IEC/local requirements and at the Investigator's discretion.

4.3. Exclusion Criteria

Subjects who meet *any* of the following exclusion criteria are not to be enrolled in this study.

- 1) Prior Tenofovir DF therapy; subjects may have received prior interferon or oral anti-HBV nucleoside/nucleotide therapy (subjects experienced on interferon must have discontinued

therapy for a minimum of six months; treatment-experienced subjects receiving oral anti-HBV nucleoside/nucleotide treatment at screening should continue their current treatment regimen until Tenofovir DF is initiated (i.e., to prevent ALT flare))

- 2) Sexually-active males or females of reproductive potential who are not willing to use an effective method of contraception during the study. (see [Appendix 5](#) for further details).
- 3) Females who are pregnant or breastfeeding, or females who wish to become pregnant during the course of the study.
- 4) Known hypersensitivity to Tenofovir DF, the metabolites or formulation excipients
- 5) Any condition (including alcohol or substance abuse) or prior therapy that, in the opinion of the Investigator, would make the subject unsuitable for the study or unable to comply with treatment requirements

5. ADMINISTRATION OF TENOFOVIR DF TREATMENT

5.1. Randomization, Blinding and Treatment Codes

After screening and once eligibility has been confirmed, subjects will be assigned a subject number and monitoring arm (i.e., Group 1 or Group 2). A centralized procedure will be used, to assign subjects to the respective monitoring arm. For the 96 weeks of the study, Tenofovir DF will be dispensed to the subject in numbered bottles from supplies stored at the study site. Tenofovir DF monitoring groups will be randomly allocated, but the allocation to one or the other group will not be blinded. Subjects will be informed of the two monitoring groups at the time of study screening and informed of their assignment to one of the two selected CHB management monitoring groups after consent is obtained at the subject's screening appointment.

All Baseline tests and procedures must be completed prior to the administration of the first dose of Tenofovir DF. Initiation of treatment with Tenofovir DF should take place within 24 hours of the Baseline Visit.

For duration of the study, Tenofovir DF 300mg will be supplied by Gilead.

5.1.1. Procedures for Breaking Treatment Codes:

Not applicable

5.2. Description and Handling of Tenofovir DF

5.2.1. Formulation

Tenofovir DF tablets are light blue, almond-shaped, film-coated tablets containing 300mg of Tenofovir disoproxil fumarate (equivalent to 245mg Tenofovir disoproxil). Each tablet contains the following inactive ingredients: microcrystalline cellulose, lactose monohydrate, pregelatinized starch, croscarmellose sodium, and magnesium stearate. The Tenofovir DF tablets are film-coated to mask taste. Each tablet is film-coated with a mixture of lactose monohydrate, hypromellose (hydroxypropyl methylcellulose), glycerol triacetate, titanium dioxide, and indigo carmine aluminum lake.

5.2.2. Packaging and Labeling

Tenofovir DF is packaged in white, high-density polyethylene (HDPE) bottles with a white child resistant cap. There are 30 tablets per bottle. Each bottle also contains silica gel as a desiccant to protect the product from humidity and fiber packing to protect the product during handling and shipping.

During Weeks 0 to 96, subjects will be provided with sufficient supplies for 12 weeks of dosing. At a minimum, each bottle will be labeled with a lot number, the protocol number, administration instructions, storage instructions, expiration date, Sponsor name and address. Additional information will be included according to the requirements of the protocol and local law.

5.2.3. Storage and Handling

Tenofovir DF tablets should be stored at 25°C (77°F); excursions are permitted to 15°-30°C (59°-86°F).

To ensure product stability, Tenofovir DF should not be dispensed in a container other than the one supplied.

5.3. Dosage and Administration of Tenofovir DF

Subjects will be assigned to receive one of the following treatments in an unblinded fashion:

Group 1: open-label Tenofovir DF 300mg PO once daily, enhanced monitoring

Group 2: open-label Tenofovir DF 300mg PO once daily, Tenofovir DF, local standards of care for monitoring

Subjects will be instructed to take one tablet by mouth daily. Tenofovir DF should be taken with food.

After 96 weeks of protocol-guided monitoring, each subject will switch to medical management for CHB as per local standards of care.

Active study subjects will be dispensed Tenofovir DF at baseline and through the end of the study (until each subject reaches Week 96). Subjects will be instructed to return empty containers as well as unused study medication in the original container at each study visit. The investigator will be responsible for maintaining accurate records for Tenofovir DF and Tenofovir DF bottles dispensed and returned. The inventory must be available for inspection by the study monitor. Study medication supplies, including partially used or empty bottles, must be accounted for and the dispensing logs must be verified by the study monitor prior to destruction or return.

5.4. Prior and Concomitant Medications

5.4.1. Prior to Study Entry

Refer to Exclusion Criteria in Section 4.3.

5.4.2. During the Study

Use of the following medications is prohibited while subjects are taking Tenofovir DF, and subjects should be followed closely by their providers:

- Antiviral agents with anti-HBV activity, including lamivudine, emtricitabine, entecavir, adefovir, telbivudine, clevudine, or others
- Antiviral agents associated with potential renal impairment (e.g., cidofovir, acyclovir, valacyclovir, ganciclovir, valganciclovir)

- Interferon and pegylated interferon
- Nephrotoxic agents (e.g., aminoglycoside antibiotics, cisplatin, foscarnet, IV amphotericin B, IV pentamidine, cyclosporine, tacrolimus, chronic daily non-steroidal anti-inflammatory drugs)
- Hepatotoxic agents (e.g., anabolic steroids, isoniazid, itraconazole, ketoconazole, lovastatin, rifabutin, rifampin, simvastatin)
- Competitors of renal excretion, such as probenecid
- Systemic chemotherapeutic agents
- Interleukin-2 [IL-2] and other immunomodulating agents
- Systemic corticosteroids
- Investigational agents, except with written approval of the Sponsor

All concomitant medications, including vitamin supplements, herbal remedies and hormonal contraception, must be recorded in the appropriate section of the Case Report Forms.

5.5. Devices

Not applicable

5.6. Accountability for Tenofovir DF

The investigator is responsible for ensuring adequate accountability of all used and unused Tenofovir DF. This includes acknowledgement of receipt of each shipment of Tenofovir DF (quantity and condition). All used and unused Tenofovir DF dispensed to subjects must be returned to the site.

Tenofovir DF accountability records will be provided to each study site to:

- Record the date received and quantity of Tenofovir DF
- Record the date, subject number, subject initials, the Tenofovir DF lot numbers dispensed
- Record the date, quantity of used and unused Tenofovir DF returned, along with the initials of the person recording the information.

5.6.1. Tenofovir DF Return or Disposal

At study initiation, the monitor will evaluate the site's standard operating procedure for drug disposal/destruction in order to ensure that it complies with Gilead requirements. Drug may be returned or destroyed on an ongoing basis during the study if appropriate. At the end of the study, following final drug inventory reconciliation by the monitor, the study site will dispose of and/or destroy all unused drug supplies, including empty containers, according to these procedures.

All drug supplies and associated documentation will be periodically reviewed and verified by the study monitor over the course of the study.

6. STUDY PROCEDURES

The study procedures to be conducted for each subject enrolled in the study are presented in tabular form in [Appendix 2](#) and described in the text that follows.

The investigator must document any deviation from protocol procedures and notify the study sponsor or contract research organization (CRO).

6.1. Subject Enrollment and Treatment Assignment

The study population will consist of HBV-infected adolescents who are between 12 to <16 years of age at the commencement of the study and receiving Tenofovir DF for the treatment of CHB during study treatment. The study population will also be enrolled through one of the approximately 25 participating European clinics across several countries (eg., Bulgaria, Poland, Romania, Italy, France, Spain, and the United Kingdom) projected to commence in June 2015.

Eligibility criteria will include a confirmed diagnosis of HBV infection in subjects who are Tenofovir DF treatment naïve. At screening, adolescent subjects (12 to <16 years of age) with documented chronic hepatitis B (e.g HBsAg-positive for ≥ 6 months), weighing ≥ 35 kg will be eligible for the study.

Subjects must be naïve to Tenofovir DF, but could have received interferon or any oral anti-HBV nucleosides/nucleotide therapy. Subjects experienced on oral anti-HBV nucleoside/nucleotide therapy must have discontinued therapy prior to screening. Subjects must have discontinued interferon at least six months prior to screening.

Data will be collected from subjects prospectively from initial enrollment into the study (baseline) and up to 96 weeks, study completion, loss to follow-up or death, whichever occurs first. Subjects who discontinue Tenofovir DF as a consequence of an AE will be monitored for up to 6 months from the date of the observed AE.

The data will contain medical records, demographics, diagnoses, procedures, medications, and laboratory tests (including DEXA).

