This is an interventional study involving two assigned monitoring groups of chronic HBV infected adolescents who will receive treatment with open-label, market-authorized Tenofovir DF and followed prospectively to a primary endpoint at 96 weeks. Subjects will be assigned to one of two monitoring groups (Group 1 or 2); subjects in both groups will follow pre-set schedules for bone and bone biomarker monitoring. Group 1 will receive more frequent BMD, bone biomarker, and renal function monitoring compared to Group 2 over the 96 week period. Subjects will be assigned but not blinded to one of the two monitoring groups.

Number of Subjects Planned:

100 subjects to receive treatment with Tenofovir DF and assigned to one of two monitoring groups (50 in each group)

Target Population:

Adolescents aged 12 to <16 years at the time of enrollment who are diagnosed with CHB and are Tenofovir DF treatment naïve

Duration of Treatment:

Subjects will be treated for 96 weeks with Tenofovir DF treatment

Diagnosis and Main Eligibility Criteria:

At screening, CHB subjects aged 12 to <16 years of age (e.g., HBsAg-positive for at least 6 months), weighing ≥ 35 kg will be eligible for the study. Subjects must be naïve to Tenofovir DF, but could have received interferon or any oral anti-HBV nucleoside/nucleotide therapy. Subjects experienced on interferon must have discontinued therapy for a minimum of six months; treatment-experienced subjects receiving oral anti-HBV nucleoside/nucleotide treatment at screening must continue their current treatment regimen until Tenofovir DF is initiated; subjects previously treated with an oral anti-HBV nucleoside/nucleotide should initiate Tenofovir DF without a treatment washout period to prevent ALT flare. Pregnant or breastfeeding females will not be eligible for the study.

Study Procedures/
Frequency:

Screening measures for Groups 1 and 2 will include determining a subject's eligibility into the study with the following criteria: current age, documentation of chronic HBV infection (e.g., positive laboratory results for HBsAg for at least 6 months prior to screening, a medical assessment affirming CHB status), ability to swallow solid tablets, likelihood of adherence to treatment regimen, obtaining written informed consent from subject's parent or legal guardian or obtaining informed assent from the subject.

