6.2. Pre-treatment Assessments

6.2.1. Screening Visit

Subjects will be screened within 30 days before assignment to determine eligibility for participation in the study. The following will be performed and documented at screening:

- 1) Obtain written informed consent
- 2) Obtain medical history
- 3) Complete physical examination including, vital signs, body weight, and height

- 4) Screen for pregnancy (serum screen) and contraceptive use
- 5) Conduct preliminary liver chemistry tests (ALT, ALP, AST, total and direct bilirubin, total protein, albumin, GGT, LDH, CK), serum renal chemistry (glucose, creatinine, creatinine clearance (calculated), magnesium, bicarbonate, chloride, potassium, sodium) and urinalysis (glucose, protein, creatinine, phosphate, bicarbonate, blood, calcium) (to be averaged with Baseline renal chemistry values), fasting required
- 6) HBV serology (HBeAg and HBsAg; anti-HBe and anti-HBs (if Ag negative))

Subjects meeting all of the inclusion criteria and none of the exclusion criteria will return to the clinic within 30 days after screening for commencement into the study.

From the time of obtaining informed consent through the first administration of Tenofovir DF, record all renal and bone AEs and any SAEs (not limited to bone or renal) on the adverse events case report form (CRF/eCRF). All other untoward medical occurrences observed during the screening period, including exacerbation or changes in medical history are to be captured on the medical history CRF/eCRF. See Section 7 Adverse Events and Toxicity Management for additional details.

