6.3. Baseline Visit

The Baseline Visit should occur within 30 (\pm 3) days of the initial Screening Visit. All baseline tests and procedures should be completed prior to the receipt of the first dose of Tenofovir DF. Subjects will be dispensed Tenofovir DF medication at their Baseline Visit. Tenofovir DF should be initiated within 24 hours of the Baseline Visit.

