7.5.7. Management of ALT Flares

Flares on treatment: Spontaneous exacerbations in CHB are relatively common and are characterised by transient increases in serum ALT. After initiating antiviral therapy, serum ALT may increase in some patients. In patients with compensated liver disease, these increases in serum ALT are generally not accompanied by an increase in serum bilirubin concentrations or hepatic decompensation. Patients with cirrhosis may be at a higher risk for hepatic decompensation following hepatitis exacerbation, and therefore should be monitored closely during therapy.

Flares after treatment discontinuation: Acute exacerbation of hepatitis has also been reported in patients who have discontinued HBV therapy. Post-treatment exacerbations are usually associated with rising HBV DNA, and the majority appears to be self-limited. However, severe exacerbations, including fatalities, have been reported. Hepatic function should be monitored at repeated intervals with both clinical and laboratory follow-up for at least 6 months after

discontinuation of HBV therapy. If appropriate, resumption of HBV therapy may be warranted. In patients with advanced liver disease or cirrhosis, treatment discontinuation is not recommended since post-treatment exacerbation of hepatitis may lead to hepatic decompensation. Patients should be placed on commercially available HBV therapy following study drug discontinuation. Liver flares are especially serious, and sometimes fatal in patients with decompensated liver disease.

On-Treatment ALT Flare and Post-Treatment Exacerbation of Hepatitis are defined as:

- Serum ALT $> 2 \times$ baseline and $> 10 \times$ ULN, with or without associated symptoms OR
- Confirmed ALT elevation (defined as 1-grade shift or $2 \times$ previous value) associated with confirmed changes outside of the normal range in other laboratory parameters suggestive of worsening hepatic function (total bilirubin ≥ 2 mg/dL above baseline, abnormal PT ≥ 2 seconds or INR ≥ 0.5 over baseline, abnormal serum albumin ≥ 1 g/dL below baseline or elevated serum lactate levels (if available), defined as $2 \times$ ULN per the Adult AIDS Clinical Trials Group (AACTG) guidelines).

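### Protocol Section 6.1 requires oral anti-HBV therapy to be stopped before screening, whereas the synopsis, exclusion criterion 1 and the SAP keep current users on it until tenofovir DF starts

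*Protocol*

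**What the plan says.** Four places set a timing rule for prior oral anti-HBV nucleoside/nucleotide therapy.

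- **Protocol 6.1 (Subject Enrollment and Treatment Assignment):** "Subjects experienced on oral anti-HBV nucleoside/nucleotide therapy must have discontinued therapy prior to screening". The next sentence sets the six-month interferon rule, and the preceding paragraph introduces eligibility criteria.
- **Protocol synopsis (Diagnosis and Main Eligibility Criteria):** "treatment-experienced subjects receiving oral anti-HBV nucleoside/nucleotide treatment at screening must continue their current treatment regimen until Tenofovir DF is initiated". It adds that subjects previously treated with an oral agent "should initiate Tenofovir DF without a treatment washout period to prevent ALT flare".
- **Protocol 4.3, exclusion criterion 1:** treatment-experienced subjects on oral therapy at screening "should continue their current treatment regimen until Tenofovir DF is initiated (i.e., to prevent ALT flare").
- **SAP 1.2 (Key Eligibility Criteria):** repeats the criterion 1 rule with the same reason.

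Two other sections bear on which rule governs. Section 5.4.1, on medication before study entry, says only "Refer to Exclusion Criteria in Section 4.3". Section 6.2.1 says "Subjects meeting all of the inclusion criteria and none of the exclusion criteria will return to the clinic within 30 days after screening". Section 3.2 allows prior oral therapy but gives no timing rule for it.

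**The concern.** Section 6.1 uses mandatory language in the part of the protocol that tells sites how to enrol. Applied to an adolescent on oral therapy at screening, it leads to one of two results. The site may exclude a subject whom criterion 1 admits, in a study that says its pool of eligible patients is limited. Or the subject may enter after a period off treatment, which the synopsis rules out.

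Section 7.5.7 describes the hazard of the second route. It says most post-treatment exacerbations appear to be self-limited, but also that "severe exacerbations, including fatalities, have been reported", and it advises against stopping treatment in advanced liver disease or cirrhosis. Section 4.3 has no specific exclusion for either condition; only the investigator-judgment criterion would cover them.

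**Working it through.** The plan gives no figure to reproduce. The check is a comparison of text, followed by simple arithmetic on the length of the possible gap.

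**Step 1: can one subject meet both rules?** Take a subject on oral therapy on the day of screening.

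| Source | What it requires of this subject | Strength |
|---|---|---|
| Protocol 6.1 | Already stopped before screening | must |
| Protocol synopsis | Continue until tenofovir DF starts | must |
| Protocol 4.3, criterion 1 | Continue until tenofovir DF starts | should |
| SAP 1.2 | Continue until tenofovir DF starts | should |

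The subject fails 6.1 by being on therapy, and departs from the other three by coming off it. The difference between must and should does not change this.

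**Step 2: does a narrower reading of 6.1 help?** It could be read as covering past users only. But the sentence covers all subjects experienced on oral therapy and makes no exception for current users. The synopsis, criterion 1 and the SAP all describe current users as treatment-experienced. Section 5.4.2, which bars other anti-HBV agents, applies only while subjects are taking tenofovir DF, so it does not reconcile the rules either.

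**Step 3: how long could the gap be?** The inputs are:

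- Section 6.2.1: return within 30 days after screening. The SAP (1.2) also gives a 30-day screening period.
- Section 6.3: Baseline Visit within 30 (± 3) days of screening.
- Section 6.3: "Tenofovir DF should be initiated within 24 hours of the Baseline Visit", so up to 1 further day.

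Longest interval = longest screening-to-baseline time + 1 day.

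- By 6.2.1 and the SAP: 30 + 1 = 31 days.
- By 6.3: (30 + 3) + 1 = 34 days.

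Untreated gap under 6.1 = actual screening-to-first-dose interval + time off therapy before screening. The first term is at most about 31 to 34 days and may be shorter; 6.1 sets no limit on the second. Planned gap under the synopsis and criterion 1 = 0 days.

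**Step 4: how many subjects?** Only those on oral therapy at or shortly before screening are affected. Neither document gives their number. SAP 1.4 reports 30 enrolled, so the range is 0 to 30, plus any excluded at screening.

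**Step 5: which consequence is more likely?** Consent is obtained at the Screening Visit (6.2.1) and must precede any study-related procedure (8.12.3). Stopping therapy before screening in order to qualify would therefore happen before consent. Exclusion is the more direct result of the sentence; the untreated gap is the less direct one.

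**The case against.** The strongest reply is that the documents already show which rule governs. The numbered criteria are in Sections 4.2 and 4.3, Section 6.2.1 admits subjects on those criteria, Section 5.4.1 sends prior-medication questions to Section 4.3, and the SAP repeats the Section 4.3 rule. On this view 6.1 is one stray sentence in a narrative recap, and a site working from the numbered list reaches the right answer.

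Much of this stands. The 6.1 sentence is the outlier, and a careful site would probably not be misled. No document shows a wrongful exclusion or a flare, or links the sentence to low enrolment. Liver chemistry was also to be checked at both screening and baseline. The day counts are ceilings, not estimates of gaps that occurred, and 0 to 30 is simply the whole possible range.

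It does not remove the conflict. The protocol has no clause saying which section prevails. Section 6 is introduced as the procedures to be carried out for each subject, and its wording on this point is stronger than that of criterion 1.

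**Conclusion.** The contradiction is real and Section 6.1 is wrong as written. For a subject on oral therapy at screening it reverses a safety instruction given consistently in three other places. The planned gap is 0 days; following 6.1 would put the screening-to-first-dose interval, at most about 31 to 34 days, off treatment, together with any earlier time off therapy.

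The effect is confined to subjects on oral therapy at or near screening, whose number is not given. The percent-change and 4%-decrease bone mineral density analyses are not affected. The conclusion rests on reading 6.1 literally and assumes nothing about what sites actually did. It should be corrected, but it does not threaten the study's results.

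**What to change.** Replace the 6.1 sentence with the exclusion criterion 1 rule, that subjects on oral anti-HBV therapy at screening "should continue their current treatment regimen until Tenofovir DF is initiated (i.e., to prevent ALT flare"). Add the synopsis instruction that they "should initiate Tenofovir DF without a treatment washout period to prevent ALT flare". In the synopsis that clause refers to subjects previously treated with an oral agent, so the new text should say explicitly that it applies to those still on therapy at screening.

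SAP 2.1 puts the last patient's last visit in April 2018, so the practical step is one line in the study report. It should record the 6.1 sentence as a protocol error and state that Section 4.3 was the intended rule.

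Optionally, show in Listing 8 (Prior Hepatitis B Medications) whether each subject was still on oral therapy at baseline, where stop dates allow. Protocol 3.6 and 8.12.5 require start and end dates for concomitant medications in source records, but the documents do not show that stop dates for prior hepatitis B drugs reached the study database.

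The cost is one sentence or one erratum line, with no new data collection.
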